### 2.2.1.3.3. SAE Estimands

SAE estimands have the same attributes (treatment condition, population, intercurrent events, population-level summary) as AE estimands (Section 2.2.1.3.2), except:

- **Variables:** Any SAEs reported throughout the study ([Section 3.1.3.3](#)).

### 2.2.1.3.4. NDCMC Estimands

NDCMC estimands have the same attributes (treatment condition, population, intercurrent events, population-level summary) as AE estimands (Section 2.2.1.3.2), except:

- **Variables:** Any NDCMCs reported throughout the study ([Section 3.1.3.3](#)).

### 2.2.1.4. Substudy B Primary Safety Estimands

#### 2.2.1.4.1. Reactogenicity Estimands

Reactogenicity estimands have the following 5 attributes:

- **Treatment condition:** RSVpreF received in Substudy B.
- **Population:** Participants as defined by the study inclusion/exclusion criteria for Substudy B.
- **Variables:** Each item included in the e-diary from Days 1 through 7 after each dose or any dose (refer to [Section 3.1.3.1](#) and [Section 3.1.3.2](#)).
- **Intercurrent events:** All data collected after the intercurrent events will be included.
- **Population-level summary:** The rates of reporting each reactogenicity item.

#### 2.2.1.4.2. AE Estimands

AE estimands have the same attributes (treatment condition, population, intercurrent events, population-level summary) as reactogenicity estimands (Section 2.2.1.4.1), except:

- **Variables:** AEs reported within 1 month after each dose or any dose ([Section 3.1.3.3](#)).

#### 2.2.1.4.3. SAE Estimands

SAE estimands have the same attributes (treatment condition, population, intercurrent events, population-level summary) as reactogenicity estimands (Section 2.2.1.4.1), except:

- **Variables:** SAEs reported throughout the study (Section 3.1.3.3).

#### 2.2.1.4.4. NDCMC Estimands

NDCMC estimands have the same attributes (treatment condition, population, intercurrent events, population-level summary) as reactogenicity estimands (Section 2.2.1.4.1), except:

- **Variables:** NDCMCs reported throughout the study (Section 3.1.3.3).

### 2.2.2. Secondary Estimands

The secondary estimands for immunogenicity objectives will use the hypothetical strategy and describe the RSVpreF immune response in participants without the intercurrent events. In other words, the immune response is estimated in the hypothetical setting where participants follow the study schedule and protocol requirements as directed.

#### 2.2.2.1. Substudy A Secondary Immunogenicity Estimands

##### 2.2.2.1.1. Secondary RSV NT Immunogenicity Estimands

- **Treatment condition:** Randomized to RSVpreF or placebo in Study C3671023 Substudy A.
- **Population:** Participants as defined by the study inclusion/exclusion criteria for Substudy A.
- **Variables:** RSV serum NTs for subgroup A and subgroup B measured at 1 month after vaccination with RSVpreF.
- **Intercurrent events:** The following intercurrent events could impact the interpretation or the measurement of the immune response:
  1. The participant did not receive the vaccine as randomized in Substudy A.
  2. The participant did not meet the study inclusion criteria or did meet the exclusion criteria for Substudy A.
  3. Major protocol violations: The participant received a prohibited vaccine or treatment that may alter the immune response.
  4. Blood was taken outside an acceptable window for immunogenicity evaluation (<27 days or >42 days after vaccination with RSVpreF or placebo).

The clinical question of interest is the immune response elicited from RSVpreF in young adults ( $\geq 18$  to  $< 60$  years of age) without any influence from any other immune-modifying drugs or vaccines and measured within a homogeneous time window. Therefore, all data after intercurrent events 1, 2, and 3, as well as all data at intercurrent event 4, if collected, will be excluded. Major protocol violations will be determined by clinical review.

- **Population-level summary:** GMT of NT before vaccination and 1 month after vaccination, and GMFR of NT 1 month after vaccination.

### 2.2.3. Additional Estimands

Additional estimands, as supplemental analyses to support the primary and secondary immunogenicity objectives, are defined. The table below lists the strategies for addressing intercurrent events, which are listed in [Section 2.2.1.1](#), [Section 2.2.1.2](#), and [Section 2.2.2](#) for the immunogenicity objectives. The remaining estimand attributes are the same for each objective.

Immunogenicity Objective	Intercurrent Event Handling Strategy
Substudy B primary immunogenicity	Treatment policy
Substudy A secondary immunogenicity	Treatment policy

## 2.3. Study Design

This is a Phase 3 study to assess the safety, tolerability, and immunogenicity of Pfizer's RSVpreF in adults at high risk of severe RSV disease. The study will consist of 2 substudies: Substudy A and Substudy B. Each substudy design is detailed separately as follows.

### Substudy A Design

This is a Phase 3, multicenter, randomized, double-blinded, placebo-controlled study that will assess the safety, tolerability, and immunogenicity of Pfizer's RSVpreF in adults  $\geq 18$  to  $< 60$  years of age considered to be at high risk of RSV disease due to certain chronic medical conditions.

Approximately 675 participants  $\geq 18$  to  $< 60$  years of age considered at high risk of RSV disease due to certain chronic medical conditions, excluding immunocompromising conditions, will be randomized to receive 1 dose of RSVpreF or placebo in a 2:1 ratio.

All participants will have blood drawn at baseline prior to vaccination and at 1 month after vaccination to assess immunogenicity. Immunogenicity elicited at 1 month after vaccination with RSVpreF in Substudy A will be bridged to the immunogenicity of participants  $\geq 60$  years of age in the C3671013 efficacy study, in which RSVpreF efficacy was demonstrated.

Local reaction and systemic event data will be collected in an e-diary for 7 days after study vaccination (Days 1 through 7, where Day 1 is the day of vaccination). Reported Grade 3 reactogenicity will be assessed by the study site to determine if an unscheduled visit is required.

For all participants, AEs will be collected from informed consent through 1 month following study intervention administration, and NDCMCs and SAEs will be collected from informed consent throughout study participation. In addition, AEs occurring up to 48 hours after blood draws that are related to study procedures will be collected. AESIs will be collected throughout the study.

## **Substudy B Design**

This is a Phase 3, single-arm, open-label, multicenter study that will assess the safety, tolerability, and immunogenicity of Pfizer's RSVpreF in immunocompromised adults.

Approximately 200 immunocompromised adults  $\geq 18$  years of age will receive 2 doses of RSVpreF with an interval of 1 month. Approximately 100 participants will be  $\geq 60$  years of age and approximately 100 participants will be  $\geq 18$  to  $< 60$  years of age. All participants will have blood drawn at baseline prior to vaccination and at 1 month after (each) vaccination to assess immunogenicity.

Local reaction and systemic event data will be collected in an e-diary for 7 days after study vaccination (Days 1 through 7, where Day 1 is the day of vaccination). Reported Grade 3 reactogenicity will be assessed by the study site to determine if an unscheduled visit is required.

For all participants, AEs will be collected from informed consent through 1 month following study intervention administration, and NDCMCs and SAEs will be collected from informed consent throughout study participation. In addition, AEs occurring up to 48 hours after blood draws that are related to study procedures will be collected. AESIs will be collected throughout the study.

## **3. ENDPOINTS AND BASELINE VARIABLES: DEFINITIONS AND CONVENTIONS**

### **3.1. Primary Endpoints**

#### **3.1.1. Substudy A Primary Immunogenicity Endpoint**

RSV A- and RSV B-neutralizing antibody titers will be determined on sera collected before vaccination and at the 1-month postvaccination visit. NT data collected from Substudy A will be concurrently tested with the sera collected from C3671013 immunogenicity subset RSVpreF recipients at both the prevaccination visit and the 1-month postvaccination visit.

Titers above the LLOQ are considered accurate and their quantitated values will be reported. Refer to [Section 5.3.2](#) for LLOQ details. Titers below the corresponding LLOQ, or denoted as BLQ, will be set to  $0.5 \times$  LLOQ for analysis. Missing assay results will not be imputed.

In addition, RSV seroresponse after vaccination will be defined for each participant for subgroup A and subgroup B respectively:

- If prevaccination results are  $\geq$  LLOQ, seroresponse is achieved if there is a  $\geq 4$ -fold rise from prevaccination results.
- If prevaccination results are below LLOQ, seroresponse is achieved if the postvaccination titer is  $\geq 4 \times$  LLOQ.

### 3.1.2. Substudy B Primary Immunogenicity Endpoint

RSV A– and RSV B–neutralizing antibody titers will be determined before the first dose, before the second dose, and 1 month after the second dose for Substudy B.

Titers above the LLOQ are considered accurate and their quantitated values will be reported. Refer to [Section 5.3.2](#) for LLOQ details. Titers below the corresponding LLOQ, or denoted as BLQ, will be set to  $0.5 \times$  LLOQ for analysis. Missing assay results will not be imputed.

RSV A and RSV B NTs at each blood sampling time point are included in the assay result data, thus no derivation is needed. The following variables will be derived for each participant:

1. RSV A/B at each blood sampling time point: This will be derived as the geometric mean of RSV A and RSV B NTs measured at each blood sampling time point for each participant.
2. RSV A, RSV B, and RSV A/B NT fold rise: This will be derived from before vaccination to each applicable postvaccination visit. The numerator is the postvaccination value and the denominator is the prevaccination value.

When calculating a fold rise, if assay results are  $<$  LLOQ, the assay results will be converted to  $0.5 \times$  LLOQ, except when the prevaccination assay result is  $<$  LLOQ while the postvaccination result is  $\geq$  LLOQ, in which case the prevaccination value will be set to LLOQ.

### 3.1.3. Primary Safety Endpoints for Substudy A and Substudy B

Primary safety endpoints include both reactogenicity data and AEs collected from the e-diary and AE CRF.

Based on feedback from the FDA on multiple vaccine programs, reactogenicity data will utilize both e-diary data (prompted local reactions and systemic events) and reactogenicity events reported in the AE CRF during the e-diary collection period. Since the AE CRF did not designate a specific page to collect reactogenicity data for an untransmitted e-diary, Pfizer has adopted a process of providing a listing of AEs reported within 7 days after vaccination to the clinical team to review and determine (“flag”) which PTs should be considered reactogenicity events before the database lock. AEs reported on the same day of vaccination but missing the AE start time are defaulted to AEs reported after vaccination.

Following these review steps, those AEs reported within 7 days after vaccination that match with those flagged PTs will be considered reactogenicity data. If the same reactogenicity events are reported on the same day from both the e-diary and the AE CRF, the highest grade from the 2 data sources will be used for that specific day for analysis.

It should be noted that the data collection in the AE CRF is different from that of the e-diary:

- For redness, swelling, and fever, the measured size of redness and swelling at the injection site and temperature are recorded in the e-diary, but not in the AE CRF. As the missing e-diary entries are monitored with ongoing review of the prompted reactions reported in the AE CRF, any measurement recorded in the query response will be taken into consideration for the primary analysis using the data handling memo for analysis purposes. For the 7 days, only the maximum grading from both sources will be used for the aggregated severity analysis.
- For pain at the injection site and all other systemic events, the severity grading algorithm for the e-diary data and the AE CRF may not be the same, though Pfizer will choose the highest-severity grade.

If a participant did not have any e-diary data transferred within 7 days after vaccination, the AE CRF data in general will not be used for derivation, because this may inflate the denominator and bias the analysis, since participants who did not transfer e-diary data may be less likely to report reactogenicity. If a participant did not report any e-diary data, the participant will not be included in the analysis of reactogenicity data.

The subsections below describe how to derive each safety endpoint. Since the derivation is similar between Substudy A and Substudy B, no separate subsection is needed for each substudy.

### **3.1.3.1. Local Reactions Within 7 Days After Vaccination**

The local reactions include redness, swelling, and pain at the injection site from Day 1 through Day 7 after vaccination, where Day 1 is the day of vaccination with RSVpreF or placebo. Any reported reactogenicity events in the AE CRF during the e-diary collection period are included in the derivation discussed in the following section.

This section describes derivations with details for the assessment of local reactions: any presence, maximum severity, duration, and onset day of local reactions, in addition to the presence of local reactions on each day, for each vaccine group as mentioned above.

#### **3.1.3.1.1. Presence of Local Reactions Within 7 Days After Vaccination**

For the summary of the presence (yes or no) of a local reaction during the interval from Day 1 through Day 7 after vaccination, the following 2 variables are derived for each participant included in the reactogenicity subset:

1. Presence (yes or no) of each local reaction on any day (Day 1 through Day 7) for each dose.

2. Presence (yes or no) of each local reaction on any day (Day 1 through Day 7) for any dose. This is for Substudy B only.

The derivation is described in Table 2.

**Table 2. Derived Variables for Each Local Reaction**

Variable a	Yes (1)	No (0)	Missing (.)
Any day (Days 1-7) for each dose	The participant reports the reaction as “yes” on any day (Days 1-7) for the dose.	The participant reports the reaction as “no” on all 7 days or as a combination of “no” and missing on all 7 days for the dose.	The participant reports the reaction as missing on all 7 days for the dose.
Any day (Days 1-7) for any dose (Substudy B only)	The participant reports the reaction as “yes” on any day (Days 1-7) for any dose.	The participant reports the reaction as “no” on all 7 days or as a combination of “no” and missing on all 7 days for any dose.	The participant reports the reaction as missing on all 7 days for any dose.

a. The variable will be defined for each of the 3 local reactions.

1. Presence (yes or no) of any local reaction on any day (Day 1 through Day 7) for each dose.
2. Presence (yes or no) of any local reaction on any day (Day 1 through Day 7) for any dose. This is for Substudy B only.

For any local reaction on any day, a similar definition can be applied as given in Table 3.

**Table 3. Derived Variables for Any Local Reaction**

Variable	Yes (1)	No (0)	Missing (.)
Any day (Days 1-7) for each dose	The participant reports any local reaction as “yes” on any day (Days 1-7) for the dose.	The participant reports all reactions as “no” on all 7 days or as a combination of “no” and missing on all 7 days for all 3 local reactions for the dose.	The participant reports all local reactions as missing on all 7 days for the dose.
Any day (Days 1-7) for any dose (Substudy B only)	The participant reports any local reaction as “yes” on any day (Days 1-7) for any dose.	The participant reports all reactions as “no” on all 7 days or as a combination of “no” and missing on all 7 days for all 3 local reactions for any dose.	The participant reports all local reactions as missing on all 7 days for any dose.

### 3.1.3.1.2. Maximum Severity of Local Reactions Within 7 Days After Vaccination

The grading of local reactions is listed in [Table 4](#).

3. Maximum severity of any local reaction on any day (Day 1 through Day 7) for each dose.
4. Maximum severity of any local reaction on any day (Day 1 through Day 7) for any dose.  
This is for Substudy B only.

The maximum severity for any local reaction after each vaccination will be derived as follows:

- = Missing, if values are missing for all days (Day 1 through Day 7) across all 3 local reactions
- = 0, if the participant reports all reactions as “no” or a combination of missing and “no” for all days (Day 1 through Day 7) for all individual local reactions
- = *Highest grade* (maximum severity) within 7 days after vaccination, if the answer is not “no” for at least 1 day for at least 1 local reaction

For Substudy B, the maximum severity for any local reaction after any dose will be derived after any RSVpreF dose, based on the variable of the maximum severity for any local reaction for each dose.

#### **3.1.3.1.3. Duration of Each Local Reaction**

The duration of each local reaction will be calculated in days as the resolution date of reaction - start date of reaction + 1. Resolution of the event is the last day on which the event is recorded in the e-diary (or AE CRF) or the date the event ends if it is unresolved during the participant e-diary recording period (end date collected on the CRF) or AE stop date, whichever is longer, unless chronicity is established. If there is no known end date, the duration will be considered unknown and set to “missing.” Participants with no reported reaction have no duration.

For Substudy B, as it includes 2 doses, the date that the reaction ended for 1 dose should not be after the subsequent dose. Therefore, if a reaction is ongoing at the time of a subsequent dose, the end date for the reaction after the previous vaccination would be the day before the subsequent dose date, which will be used for the duration computation.

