8.3.4. Electronic Diary for Reactogenicity

Participants will be required to complete a reactogenicity e-diary, through an application installed on a provisioned device or on the personal device of the participant, and will be asked to monitor and record local reactions, systemic events, and temperature each evening for 7 days from the day of administration of study intervention (reactogenicity period). Participants will receive reminders to complete the reactogenicity e-diary on a daily basis, starting on the day of study intervention administration (Day 1) through Day 7.

The e-diary allows recording of these assessments only within a fixed time window each day, thus providing the accurate representation of the participant's experience at that time.

Data on local reactions, systemic events, and temperature recorded in the e-diary will be transferred electronically to the e-diary vendor, where they will be available for review by investigators, their qualified designees, and sponsor staff at all times via an internet-based portal. At intervals agreed to by the vendor and Pfizer, these data will be transferred electronically to Pfizer for analysis and reporting. These data do not need to be recorded by the investigator in the CRF, except for the following conditions:

- Grade 4 local reactions will be collected on the AE CRF and assessed by the investigator using the AE intensity grading scale as detailed in [Section 10.2.3](#).
- Any local reactions or systemic events occurring within the first 30 minutes after study vaccination must be recorded on the AE page of the CRF.
- If a participant withdraws because of prompted events recorded in the e-diary, the event(s) should be recorded on the AE page of the CRF, regardless of whether the investigator considers the event(s) to be clinically significant.

- If a participant missed reporting any day in the e-diary and reports an event to the study site instead, the event should be recorded on the AE page of the CRF.
- The investigator or designee must obtain stop dates for any reactions ongoing on the last day that the e-diary was completed. The stop dates should be documented in the source documents and the information entered in the CRF.

Investigators (or appropriately qualified designees) are required to review the e-diary data online at frequent intervals to evaluate participant compliance and as part of the ongoing safety review.

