- The investigator or appropriately qualified designee reviews the e-diary data online following vaccination to evaluate participant compliance and as part of the ongoing safety review.

10.7.8.4.2. Visit 102 – 1-Month Follow-Up (Clinic, 28 to 35 Days After Vaccination at Visit 101)

- Obtain details of any nonstudy vaccinations, and prohibited medications and treatments as described in [Section 10.7.6.7](#).
- Collect a blood sample of approximately 20 mL.
- Review the participant's e-diary data. Collect stop dates of any e-diary events ongoing on the last day that the e-diary was completed and record stop dates in the CRF. Any ongoing reactions must be assessed at the next contact.
- Collect the provisioned device or assist the participant with removing the study application from his or her own personal device.
- Record AEs, AESIs, SAEs, and NDCMCs as described in [Section 8.4](#).
- Complete the source documents.
- The investigator or an authorized designee completes the CRFs.

10.7.8.4.3. Visit 103 – 6-Month Safety Follow-Up (Telephone or Clinic, Within 175 to 189 Days After Vaccination at Visit 101)

- Contact the participant by telephone. This visit can be conducted as a clinic visit if the investigator deems it is necessary for the participant to be seen in person.
- Obtain details of any nonstudy vaccinations, and prohibited medications and treatments as described in [Section 10.7.6.7.1](#).

- Review ongoing reactogenicity e-diary symptoms reported as present on the last day of the e-diary and obtain stop dates. Record stop dates in the CRF if required.
- Record AESIs, SAEs, and NDCMCs as described in [Section 8.4](#).
- Complete the source documents.
- The investigator or an authorized designee completes the CRFs.

10.7.8.4.4. Unscheduled Visit for Fever or a Grade 3 or Suspected Grade 4 Reaction

See [Section 8.10](#).

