### 6.1.3.2. Supplementary Analysis

To support the assessment of reactogenicity, the endpoints below, as specified in [Section 3.1.3.1](#) and [Section 3.1.3.2](#), will be summarized per the supplemental analysis with the same analysis population:

- Duration (days) of each local reaction and each systemic event after vaccination.
- Onset day of each local reaction and each systemic event after vaccination.

The presentation of the results will include a basic descriptive summary without the 95% CIs for each group.

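### Reactions with no known end date are set to missing and Substudy B reactions cut off at Dose 2 count as completed, so the supplementary duration summary can run short

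*SAP*

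**What the plan says.** SAP 3.1.3.1.3 computes duration as resolution date minus start date plus 1. The resolution date comes from the last recorded diary or AE CRF day, the CRF end date for a reaction unresolved within the diary period, or the AE stop date, "whichever is longer, unless chronicity is established". Two rules cover reactions whose end was not observed:

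- In general: "If there is no known end date, the duration will be considered unknown" and is set to missing.
- In Substudy B, for a reaction ongoing at the next dose: "the end date for the reaction after the previous vaccination would be the day before the subsequent dose date". That date goes into the duration calculation.

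SAP 3.1.3.2 handles systemic events in a similar way. SAP 6.1.3.2 lists "Duration (days) of each local reaction and each systemic event after vaccination" as a supplementary endpoint, with a basic descriptive summary and no confidence intervals. By default (SAP 5.2.2) that means n, mean, median, standard deviation, minimum and maximum. The two reactogenicity sensitivity analyses in SAP 6.1.3.3 concern maximum severity only.

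On data collection, Protocol 8.3.4 has participants "record local reactions, systemic events, and temperature each evening for 7 days from the day of administration of study intervention", and adds: "The investigator or designee must obtain stop dates for any reactions ongoing on the last day that the e-diary was completed". At Visit 102 (Protocol 10.7.8.4.2) sites must "Collect stop dates of any e-diary events ongoing on the last day that the e-diary was completed and record stop dates in the CRF". Visit 103 (10.7.8.4.3) and Substudy B Visits 202, 203 and 204 (10.8.8.4.2 to 10.8.8.4.4) carry similar instructions.

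**The concern.** A reaction that stops within the completed diary gets its end date from the diary. An end date is therefore usually unknown only when the reaction was still present at the last observation and nobody later obtained a stop date. Such a duration is right-censored: its exact value is unknown, but a minimum is known. Setting it to missing discards that minimum, and the reactions lost tend to be longer than those kept.

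The Dose 2 rule in Substudy B treats a similar kind of reaction the other way: it keeps the minimum but presents it as an exact, completed duration. After Dose 2 there is no later dose, so an unresolved reaction with no end date becomes missing. Durations after Dose 1 and Dose 2 are then not built alike.

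At stake is a descriptive tolerability table. Its mean, and above all its maximum, can be too low, and no planned output labels the affected reactions.

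**Working it through.** **1. Which reactions are affected**

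| Reaction | What is known | Result under SAP 3.1.3.1.3 |
|---|---|---|
| Stops within the completed diary | Last diary day with the reaction | Full duration |
| Outlasts the diary, stop date obtained | CRF end date or AE stop date | Full duration, however long |
| Present on last completed diary day, no stop date | Present at least until that day | Either that day or missing; the text does not settle it |
| Present at a later visit, stop date never obtained (Substudy A, or after Dose 2 in Substudy B) | Present at least until that visit | Missing |
| Ongoing at Dose 2 (Substudy B) | Present at Dose 2 | Closed the day before, counted as completed |

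Known minimum durations, using end - start + 1:

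- Start on Day 1 and present on Day 7: 7 - 1 + 1 = 7 days. Start on Day 3: 7 - 3 + 1 = 5 days.
- Start on Day 1 and present at Visit 102, which is at the earliest 28 days after vaccination: 28 - 0 + 1 = 29 days.
- Start on Day 1 and ongoing at Dose 2, given 28 to 35 days after Dose 1: the cut-off falls 27 to 34 days after Dose 1, so the value is 28 to 35 days.
- Diary stopped on Day 2 with the reaction present: only 1 to 2 days.

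**2. Effect of deletion on the mean**

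The documents give neither an expected duration nor a rate of unknown end dates, so there is no plan figure to reproduce. All inputs here except the 7-day diary are assumptions: duration is geometric with mean m = 2, 3 or 4 days; onset o is Day 1 or Day 2; and a fraction f of the reactions present on Day 7 has no end date.

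- Share present on Day 7: P = (1 - 1/m)^(7 - o)
- Mean duration of those reactions: 7 - o + m
- Mean after deletion: [m - fP(7 - o + m)] / (1 - fP)
- Mean if they are closed on Day 7 instead: m - fP(m - 1)

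Example with m = 3, o = 1, f = 50%: P = (2/3)^6 = 0.0878 and fP = 0.0439. After deletion the mean is (3 - 0.0439 x 9) / (1 - 0.0439) = 2.72, which is 9.2% low. Closed on Day 7, it is 3 - 0.0439 x 2 = 2.91. These are the two readings of the unsettled row above: they give different tables, and both fall below the true 3.00.

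Over all six combinations of m and o:

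| f | Share of all reactions lost | Change in mean | Median |
|---|---|---|---|
| 5% to 10% | 0.1% to 2.4% | -0.2% to -3.0% | Unchanged |
| 25% | 0.4% to 5.9% | -1.2% to -7.9% | Unchanged |
| 50% | 0.8% to 11.9% | -2.4% to -16.8% | Unchanged |
| 100% | 1.6% to 23.7% | -4.8% to -38.9% | 3 to 2 days if m = 4, otherwise unchanged |

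The maximum is more exposed than the mean: if the longest reaction has no end date, the table shows the next longest one.

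**3. Why the lower bounds should not simply be averaged**

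Assume resolved reactions average 2.2 days and that 5% of all reactions are entered at a lower bound L. The mean is 0.95 x 2.2 + 0.05 x L. With L = 7 it is 2.44 and with L = 28 it is 3.49. With L = 1 or 2, as when a diary stops early, it is 2.14 or 2.19, below the 2.2 obtained by dropping them. Averaging bounds as if they were exact can move the mean either way.

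**The case against.** A reader might infer that the rule strips out reactions because they were long. It does not: a 10-day or 40-day reaction with a stop date keeps its whole duration. Sites must seek that date repeatedly, and Protocol 8.3.4.4 has a fever present on the last diary day measured daily until it resolves. What remains is failed follow-up and reactions still open at last contact. This largely stands and is why the effect is probably small. One qualification is that the schedules of activities (10.7.1.3 and 10.8.1.3) do not mark stop-date review at Visits 103 and 204, although the procedure text requires it there.

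The count is also partly visible, because n in the duration table can be set against the number reporting the reaction. That is true if such reactions are set to missing, but n would not reveal reactions closed on the last diary day or at Dose 2, and it says nothing about minimum length.

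The Dose 2 cut-off has a sensible purpose: it assigns each reaction to one dose, and it keeps a Day 1 reaction in the table at 28 to 35 days. That stands. The remaining objection is only that the value appears as completed.

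Nor is an unknown end date proof of a long reaction. Diaries can stop early, and a reaction taken from the AE CRF may lack a stop date and still have been short.

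**Conclusion.** The point holds as a minor one. For reactions whose end was not observed, the SAP either discards a known minimum or reports it as exact, and no planned duration analysis recognises the censoring. The supplementary summary can therefore understate the mean and particularly the maximum.

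The size cannot be stated, because no rate of unknown end dates is given. The calculated range rests on the geometric durations, Day 1 or 2 onset and values of f assumed above. If stop-date collection works as required, a fall of 0.2% to 3.0% in the mean (f of 5% to 10%) is the relevant part of that range, with the median unchanged.

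Two stronger conclusions are tempting. One is that the Substudy A arms will be biased by different amounts; nothing in the documents shows that unknown end dates or persistent reactions differ by arm. The other is that persistent reactions drop out of the tolerability results; they do not, because presence and maximum severity (SAP 3.1.3.1.1 and 3.1.3.1.2) make no use of the end date. No primary result changes.

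**What to change.** In SAP 3.1.3.1.3, and by reference in 3.1.3.2:

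- Replace the missing rule: where no end date is known, flag the duration as censored at the last date the reaction is known to be present.
- Flag Substudy B reactions cut off at Dose 2 as censored too.
- State whether a reaction present on the last completed diary day, with no CRF stop date, counts as resolved that day or as censored.

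In SAP 6.1.3.2, for each reaction, group and dose:

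- Report the number censored.
- Show the maximum as >= x days where it is censored.
- Give a Kaplan-Meier median, or the median with the censored count beside it. Do not average lower bounds as if they were exact durations.

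The cost is a few sentences in the SAP and one extra table column, with no new data collection. The downside is that some entries will be lower bounds.
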